## 3.5 Safety Endpoints

Safety evaluations include physical examination, vital signs, pelvic ultrasound (includes both transabdominal ultrasound [TAU] and transvaginal ultrasound [TVU]), MRI (if required), clinical laboratory tests (including hematology, chemistry, urinalysis, and lipid panel), bone mineral density (BMD) via dual energy x-ray absorptiometry (DXA) examinations, and adverse event (AE) monitoring for the entire study duration.

## 3.6 Pharmacokinetic Endpoints

Plasma concentrations of elagolix will be determined at designated visits, and the concentrations may be used to develop a population PK model. The population PK model may be linked with data from the PD endpoints for PK/PD analyses.

# 3.7 Pharmacodynamic Endpoints

LH and FSH concentrations will be determined at designated visits throughout the study and summarized. Serum  $AUC_{0-t}$  of LH and FSH will be calculated using non-compartmental methods and summarized. Serum concentrations of other endocrine hormones may be determined and summarized if useful for the interpretation of the study results. Additional PD parameters may be calculated if useful in the interpretation of the study results.

# 3.8 Biomarker Sampling

Optional whole blood, serum, and plasma samples will be collected at specified time points (Appendix D) throughout the study to evaluate known and/or novel disease-related or drug-related biomarkers. Types of biomarkers may include nucleic acids, proteins, lipids, and/or metabolites. The objective of this research is to analyze samples for biomarkers that may help to understand PCOS, related conditions, and the subject's response to elagolix. Research may also include epigenetic changes in deoxyribonucleic acid (DNA) that may associate with the subject's response to treatment or disease. Samples for ribonucleic acid (RNA) may be used to research if any genetic variants result in changes to gene expression. This research is exploratory in nature and the results may not be included with the clinical study report.

#### 4 INVESTIGATIONAL PLAN

## 4.1 Overall Study Design and Plan

This is a Phase 2, randomized, double-blind (sponsor-unblinded), 6-month, placebo-controlled, parallel group, multicenter study designed to assess the PK and PD of elagolix and to demonstrate the safety and efficacy of elagolix in women with PCOS.

The duration of the study could be up to 42 weeks, which includes an 8-week Washout (if necessary), a 6-week Screening Period, a 24-week Treatment Period, and a 30-day Post-Treatment Follow-up Period.

The Screening Period may be extended in certain circumstances (e.g., repeat TVU is needed) following consultation with the sponsor.

**Study Visits and Assessments:** Study visits for safety, efficacy, PK, and PD assessments will be scheduled as listed in the activity schedule (Appendix D). Sites will have the option to participate in sparse PK sampling of elagolix. Optional sparse PK sampling will take place on the scheduled visits at Week 1 and Week 4 of the Treatment Period, as listed on the activity schedule (Appendix D), and includes 5 lab draws over 6 hours. If sites choose not to participate in the optional sparse PK sampling, a single PK sample will be required at the scheduled visits. At other study visits (other than the optional sparse PK sampling study visits), a single PK sample will be collected as per the activity schedule.

Required intensive PD sampling of LH and FSH will occur at Baseline, and the scheduled visits at Week 1, Week 4, and Week 16 of the Treatment Period, as listed on the activity schedule (Appendix D). Required intensive PD sampling includes 7 to 9 lab draws over 3 to 4 hours (taken every 30 minutes). At other study visits (other than intensive PD study visits), a single PD sample will be collected, per the activity schedule.

Washout Period for subjects on oral contraceptives (OCPs): a 2-month Washout Period will be required for subjects who are on OCPs. Washout Period for subjects on metformin: a 1-month Washout Period will be required for subjects on metformin. A full list of Washout Periods for other medications is presented in Table 1.

During Screening, subjects will undergo procedures and activities as listed in the Activities Schedule to ensure they meet eligibility requirements.

[figure not shown]
Beginning at Screening and throughout the Treatment Period, each subject will complete an electronic daily bleeding diary. The subjects will also undergo weekly blood draws for progesterone levels. A progesterone level  $\geq$  3 ng/mL will be used to indicate ovulation.

Subjects will undergo procedures and activities as listed in the Activities Schedule at the 30-day post-treatment follow-up visit. An unscheduled visit may occur when the subject returns to the clinic at any time for the evaluation of symptoms, changes in concomitant medications, or any AEs.

The study schematic is presented in Figure 1. Further details regarding study procedures are located in the Operations Manual (Appendix F). See Section 5 for information regarding eligibility criteria. Study sites and subjects will remain blinded for the duration of the study.

Figure 1. Study Schematic

BID = twice daily; M = month; PTFU = post-treatment follow-up; QD = once daily

Some of the study visits and visit activities (including but not limited to clinical laboratory tests and concomitant medication assessment) may be conducted in the home or non-hospital/clinic environment by qualified individuals at the investigator's request and with the subject's agreement where local regulation allows.

#### Rescreening

Subjects who screen fail for this study may be rescreened. Prior to rescreening a subject, the investigator should consult with the AbbVie Therapeutic Area Medical Director (TA MD). The TA MD will determine which procedures will need to be repeated if the subject was a screen failure for this study or another AbbVie elagolix study. The subject must re-consent and meet all eligibility criteria at the time of rescreening to qualify for the study.

# 4.2 Discussion of Study Design

#### Choice of Control Group

The control group consists of subjects randomly assigned to receive placebo. No therapy is currently approved for treatment of PCOS.

#### Appropriateness of Measurements

Standard statistical, clinical, and laboratory procedures will be utilized in this study. The safety assessments used in this study are standard and generally recognized as reliable, accurate, and relevant within the context of this study design.

DXA is a standard accepted measure of BMD and will be utilized to assess the effect of elagolix therapy on BMD.

#### Suitability of Subject Population

Women 18 to 35 years of age with PCOS are selected for this study. The lower age limit (18 years) was chosen based on the youngest adult age; the upper age limit (35 years) was chosen in order to limit the study to women earlier in the disease process. No studies in females outside of the reproductive years are necessary for this proposed indication.

This study will enrich for subjects who have PCOS with menstrual abnormalities and hyperandrogenic features by using criteria for enrollment that require elevated testosterone as well as oligomenorrhea.

#### Selection of Doses in the Study

The effects of elagolix on gonadotropic and ovarian hormones were evaluated in premenopausal healthy women in 2 Phase 1 studies over 21 days in a multiple-ascending dose study (Study M12-790), and over a period of 3 months in a folliculogenesis study (Study M12-673). In these studies, the evaluated elagolix dosages ranged from 100 mg once daily (QD) to 400 mg twice daily (BID). In the 21-day multiple-ascending dose study, dose-dependent suppression of gonadotropic and ovarian hormones was observed. Based on the results from the 2 studies, elagolix exhibited partial suppression of LH up to 100 mg BID (200 mg total daily dose), and near maximal suppression at 200 mg BID and higher. However, elagolix showed differential FSH suppression compared with LH, where no or minimal suppression was observed up to 200 mg total daily dose and near maximal or maximal suppression at 200 mg BID and higher. In the 3-month folliculogenesis study, ovulatory progesterone concentrations (> 5 nmol/L) were observed more often at lower elagolix dosages (100 to 200 mg QD, 100 mg BID) correlating with higher ovulation rates. In Study M12-790, when the same total daily dose was evaluated as QD or BID (i.e., 100 mg BID versus 200 mg QD), BID regimens appeared to provide more suppression of hormones compared with QD regimens. Testosterone suppression was also observed with elagolix dosages (100 mg BID, 200 mg BID, and 300 mg BID).

Based on the totality of the data from the Phase 1 and exploratory dose-response modeling, a total daily dose range of 50 mg to 300 mg with various dosing regimens (i.e., QD and BID) would provide an opportunity to study and explore a dose range finding in women with PCOS by targeting partial suppression of LH levels without inhibition of FSH and suppressed testosterone to achieve the desired clinical endpoints in women with PCOS. The lowest effective dose that would allow establishment or improvement in menstrual regularity is desired. The upper dose range in the study would also allow evaluation of maximum ability of elagolix to achieve improvement in hyperandrogenic features.

## 5 STUDY ACTIVITIES

# 5.1 Eligibility Criteria

Subjects must meet all of the following criteria to be included in the study.

#### Consent

1. Subject has voluntarily signed and dated the informed consent form (ICF), approved by an institutional review board (IRB)/independent ethics committee (IEC), prior to any study-specific procedures including washout or screening procedures.

- 2. Subject agrees to the washout intervals for hormonal therapies, including any other medication that may require washout (Table 1) (if a subject has participated in an investigational trial with hormonal treatment, the washout interval applies as listed in Table 1).
- 3. Subject is not taking exclusionary therapies. The medications listed in Table 2 should not be taken during Washout (if applicable), Screening, Treatment Period, and Post-Treatment Follow-up Period.
- 4. Subject must be willing to comply with study-related assessments and procedures, including completion of the daily electronic diary (e-Diary) and avoid use of all hair removal procedures and products throughout the required time periods. Laser hair removal is prohibited throughout the entire duration of the study (see Operations Manual [Appendix F] Section 3.5).

#### **Demographic and Laboratory Assessments**

- 5. Adult female, 18 to 35 years of age, inclusive, at the time of Screening.
- 6. Body mass index (BMI) 18.5 to 38 kg/m², inclusive at the time of Screening
- 7. A diagnosis of PCOS with subject meeting each of the following historical criteria:
  - Clinical hyperandrogenism or biochemical hyperandrogenism based on physical examination or laboratory findings; and
  - History of ovarian dysfunction indicated by menstrual irregularity: oligomenorrhea (menstrual interval > 35 days or ≤ 8 menstrual cycles per year) or amenorrhea (no menses in 6 consecutive months or greater); and
  - Cycle length > 35 days in the 3 months prior to Baseline based on subject self-report.
- 8. Laboratory values must meet the following criteria within the Screening Period prior to the first dose of study drug:
  - Must not have FSH level > 10 IU/L
  - Elevated testosterone (total testosterone or free testosterone calculated by central laboratory)
  - Aspartate aminotransferase (AST) and alanine aminotransferase (ALT) < 3 times the upper limit of the reference range and bilirubin < 2 times the upper limit of the reference range (unless known diagnosis of Gilbert's disease).
  - Negative urine and/or serum pregnancy test(s) during the Washout (if necessary) and/or Screening Periods, and a negative urine pregnancy test immediately before administration of the first dose of study drug.
  - Subjects must have neither hepatitis B nor C based on the presence of the following:
    - Hepatitis B surface antigen (HBsAg)
    - Hepatitis C virus antibody (HCV Ab) and detectable HCV RNA
    - Equivocal viral test results should be repeated.

- No clinically significant abnormalities in clinical chemistry, hematology, or urinalysis (excluding findings associated with the disease under study).
- Screening labs may be retested once prior to Baseline; for further retesting, contact the TA MD.
- An adequate endometrial biopsy that shows no clinically significant endometrial pathology during Screening (or within 12 months prior to Screening if documentation provided) or endometrial thickness < 5 mm on Screening TVU.

- Must have a normal Papanicolaou (Pap) smear result as described in, Operations Manual (Appendix F), Pap Test Eligibility (applies to subjects ≥ 21 years of age at Screening or age at which Pap smears are routinely performed according to local guidelines).
- Must not have active pelvic inflammatory disease at the time of Screening.

#### **Subject History**

- 9. No history of irregular menstrual bleeding associated with conditions other than PCOS (e.g., uterine polyps or submucosal uterine fibroids, adenomyosis)
- 10. Must be more than 6 months post-partum, post-abortion, post-pregnancy, and post-lactation at the time of entry into the Screening Period.
- 11. Must not have had laser hair removal within the 6 months prior to Baseline.
- 12. Must not have clinically significant gynecological finding from screening ultrasound or MRI if required, including:
  - Persistent simple ovarian cyst > 5 cm in longest diameter (If the pelvic ultrasound shows a simple ovarian cyst > 5 cm and ≤ 7 cm, an ultrasound of the ovaries may be repeated in approximately 4 to 6 weeks; however, the results must be evaluated prior to Baseline and meet eligibility criteria.)
  - Complex ovarian cyst > 3.5 cm in diameter at longest point
  - Large endometrial polyp (≥ 1 cm)
  - Submucosal fibroid
  - Endometrioma > 3.5 cm in diameter (longest diameter)
- 13. Must not be pregnant or breastfeeding or planning a pregnancy until completion of the study.
- 14. Must not have any clinically significant abnormal findings on electrocardiogram (ECG) obtained during Screening.
- 15. No diagnoses of:
  - Cushing's syndrome
  - Late onset congenital adrenal hyperplasia (or elevated screening 17-OH-P); the investigator should determine the applicable reference range for the subject as noted in central laboratory report to determine subject eligibility
  - Androgen-secreting tumors (or total testosterone > 200 ng/dL at Screening)

- Uncontrolled thyroid disease (or abnormal thyroid-stimulating hormone [TSH] and tetraiodothyronine (T4) at Screening)
  - \*Note: An abnormal TSH will reflex to test T4. If the T4 result is within normal limits, the TSH test can be repeated one time. TSH and T4 must be normal prior to Baseline.
- Hyperprolactinemia (or elevated prolactin at Screening)
- Diabetes mellitus (or abnormal fasting glucose ≥ 126 mg/dL (7.0 mmol/L) or HbA1c values
   ≥ 6.5 percent (48 mmol/mol) at Screening).
- Major depression or post-traumatic stress disorder episode within 2 years prior to Screening, or a history of other major psychiatric disorder at any time (e.g., schizophrenia, bipolar disorder).
- Active malignancy or history of malignancy (except basal cell carcinoma of the skin) with or without systemic chemotherapy
- 16. No osteoporosis or other metabolic bone disease, or any condition that would interfere with obtaining adequate DXA measurements:
  - Intercurrent bone disease (e.g., osteomalacia, osteogenesis imperfecta)
  - History or presence of a condition associated with a decrease in BMD (e.g., uncontrolled hyperthyroidism, uncontrolled hyperparathyroidism, anorexia nervosa).
  - History of low-trauma hip or vertebral fractures (e.g., fracture resulting from a fall from a standing height or lower)
  - Bilateral hip replacement
  - History of spinal surgery, spinal hardware
  - Severe scoliosis
  - Subject does not meet the limits/specifications of the local DXA machine being used for this study
  - Clinically significant hypocalcemia, hypo- or hyperphosphatemia
  - Treatment with medication (excluding calcium and vitamin D) for bone disease associated with a decrease in BMD
- ☑ 17. Results of subject's Screening DXA of the lumbar spine (L1 L4) and total hip/femoral neck
  must demonstrate adequate BMD as follows:
  - Z-score ≥ -2.0
- 18. No history of:
  - A newly diagnosed, clinically significant medical condition requiring therapeutic intervention (e.g., new onset hypertension) that has not been stabilized at least 30 days prior to Baseline
  - A clinically significant medical condition anticipated to require intervention during the course of the study participation (e.g., anticipated major elective surgery)
  - An unstable medical condition making the subject an unsuitable candidate for the study in the investigator's opinion (including, but not limited to, uncontrolled hypertension, epilepsy

requiring anti-epileptic medication, unstable angina, confirmed inflammatory bowel disease, hyperprolactinemia, clinically significant infection or injury)

- Drug abuse and/or alcohol abuse within 12 months prior to Screening
- Any suicide attempts ever or answered "yes" to questions 4 or 5 on the suicidal ideation portion (referring to within the last year) of the Columbia-Suicide Severity Rating Scale (C-SSRS) when administered during Screening or prior to dosing on Study Baseline.
- 19. No surgical history of:
  - Hysterectomy
  - Unilateral or bilateral oophorectomy
  - Ovarian wedge resection or ovarian drilling as treatment for PCOS
  - Bariatric surgical procedures of any type within 12 months of Screening
  - Major surgery within 3 months prior to the initial Screening visit
  - Minor surgery within 1 month prior to the initial Screening visit
- 20. Must not be using:
  - Medications identified in Section 5.3 Table 2 during Washout, Screening, Treatment or Post-Treatment Follow-Up Periods.
  - Copper intrauterine device (CU-IUD), levonorgestrel intrauterine system (LNG-IUS), or implant. If the CU-IUD, LNG-IUS, or implant is removed, and subject completes the required washout if applicable, the subject may be considered for Screening for the study.
  - Systemic corticosteroids for over 14 days within 3 months prior to Screening or anticipate require use of systemic corticosteroids for more than 7 days during the study. Over-thecounter and prescription topical, inhaled, intranasal, or intra-articular (for occasional use) corticosteroids are allowed.
  - Oral retinoid preparations such as Accutane® (isotretinoin) within the last 12 months prior to Screening. Topical isotretinoin applications are also not permitted within the last 28 days prior to Screening.
- 21. Regarding other study participation, subjects must not be:
  - Previously treated in either an elagolix study or a study involving another investigational GnRH antagonist, within the last 3 months prior to entry into the Screening Period
  - Currently participating in another investigational study (drug or device)
  - Participating in an investigational drug study (i.e., receiving or has received investigational product) within 28 days or 5 times the investigational drug half-life, whichever is longer, prior to Screening procedures

Table 1. Washout Intervals for Exclusionary Hormonal/Anti-Hormonal Therapy

Therapy	Minimum Interval for Washout a	
Medroxyprogesterone acetate injection (Depo Provera®; Sayana®)	12 months from injection	
GnRH antagonists and GnRH agonists	3 months	
Aromatase inhibitors	3 months	
Selective progesterone receptor modulators (e.g., ulipristal acetate, vilaprisan)		
Danazol (Cyclomen®)		
Clomiphene	3 months	
Gonadotropins		
Antiandrogens		
Oral, intramuscular or intravenous glucocorticoids		
Oral contraceptives b		
Oral, transdermal, or intravaginal estrogen preparations	2 months	
Oral, intravaginal or transdermal progesterone/progestin preparations, including tibolone	2 1110111113	
Hormonal and nonhormonal IUD, sub-dermal progestin implant (e.g., Nexplanon®)	2 months after removal	
NuvaRing®		
Moderate (bosentan, efavirenz, etravirine, modafinil) or strong inducers (phenytoin, rifampin, carbamazepine, St. John's Wort, mitotane) of cytochrome P450 3A (CYP3A)		
Moderate (cimetidine, ciprofloxacin, erythromycin, fluconazole) or strong (itraconazole, ketoconazole, grapefruit juice, clarithromycin, diltiazem) inhibitors of CYP3A	1 month	
Metformin (and other insulin-sensitizing agents)		
Statins (and other lipid-lowering agents)	1	

GnRH = gonadotropin-releasing hormone; IUD = intrauterine device

- a. This is the minimum washout. If less than a full course of therapy is administered, the investigator should contact the AbbVie TA MD listed on the cover page of this protocol to discuss and confirm the required washout interval.
- b. Exception: levonorgestrel 1.5 mg or ulipristal acetate 30 mg used for emergency contraception.

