# 5.3 Prohibited Medications and Therapy

The medications listed in Table 2 should not be taken during Washout (if applicable), Screening, Treatment Period, and Post-Treatment Follow-Up Period.

Table 2. Prohibited Medications

Glucocorticoids, oral or injectable (chronic use only) Spironolactone and other antiandrogens Aromatase inhibitors Infertility treatments Clomiphene Mifepristone Selective progesterone receptor modulators (e.g., ulipristal acetat [except as emergency contraception, i.e., 30 mg] and vilaprisan) Tamoxifen Bromocriptine (Parlodel®) Cabergoline (Dostinex®) Raloxifene (Evista®, Optruma®, or generics) Bazedoxifene (Conbriza®) Aromatase inhibitors (e.g., anastrozole [Arimidex®], exemestane [Aromasin®]) Natural estrogen preparations or herbal remedies/supplements to	GnRH agonist and antagonist, such as:	GnRH agonists: Leuprolide acetate (Lupron®), nafarelin acetate
GnRH antagonists (other than study drug)  Danazol (Danocrine®, Cyclomen®)  Medroxyprogesterone acetate (Depo-Provera®, Provera®) Oral contraceptives  Estrogen preparations  Testosterone preparations  Other progestins (oral, vaginal, transdermal, implantable, intrauterine device (IUD), or LNG-IUS, except emergency contraception) hCG or hCG products  Levonorgestrel (except emergency contraception, i.e., levonorges 1.5 mg)  Glucocorticoids, oral or injectable (chronic use only)  Spironolactone and other antiandrogens  Aromatase inhibitors  Infertility treatments  Clomiphene  Mifepristone  Selective progesterone receptor modulators (e.g., ulipristal acetat [except as emergency contraception, i.e., 30 mg] and vilaprisan)  Tamoxifen  Bromocriptine (Parlodel®) Cabergoline (Dostinex®)  Raloxifene (Evista®, Optruma®, or generics) Bazedoxifene (Conbriza®)  Aromatase inhibitors (e.g., anastrozole [Arimidex®], exemestane [Aromasin®])  Natural estrogen preparations or herbal remedies/supplements to treat premenstrual or gynecological problems (e.g., soy-containing supplements, black cohosh)		(Synarel®), goserelin acetate

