(Conbriza®)  Aromatase inhibitors (e.g., anastrozole [Arimidex®], exemestane [Aromasin®])  Natural estrogen preparations or herbal remedies/supplements to treat premenstrual or gynecological problems (e.g., soy-containing supplements, black cohosh)		Bromocriptine (Parlodel®) Cabergoline (Dostinex®)
[Aromasin®])  Natural estrogen preparations or herbal remedies/supplements to treat premenstrual or gynecological problems (e.g., soy-containing supplements, black cohosh)		
treat premenstrual or gynecological problems (e.g., soy-containing supplements, black cohosh)		[6] 107F0[0] 22 (2010)
Treatments for impaired glucose Metformin or other similar medications, including diabetes		Natural estrogen preparations or herbal remedies/supplements to treat premenstrual or gynecological problems (e.g., soy-containing supplements, black cohosh)
tolerance and diabetes treatments		

Prohibited During	the Washout, Screening, and Treatment Periods	
Moderate and strong CYP3A inhibitors such as:	Moderate Inhibitors: Cimetidine Ciprofloxacin Erythromycin Fluconazole Strong Inhibitors: Itraconazole Ketoconazole Grapefruit juice Clarithromycin Diltiazem	
Moderate or strong CYP3A inducers, such as:	Strong Inducers: St. John's Wort Rifampin Carbamazepine Phenytoin Mitotane Dexamethasone, chronic use Moderate Inducers: Bosentan Efavirenz Etravirine Modafinil Nafcillin	
Strong inhibitors of organic anion transporter peptide (OATP) 1B1, such as:	Cyclosporine Rifampin (single dose)	
Oral and topical retinoids, teratogens, such as:	Isotretinoin (Accutane®), and other oral as well as topical retinoids	
Any drug known to affect bone density	Examples include first-generation antiepileptic drugs, Topiramate	
Prohibited During the Screening, Treatment, and Post-Treatment Follow-Up Periods		
Osteoporosis medications bisphosphonates, RANKL, [receptor activator of nuclear factor-κ B ligand] inhibitors, anabolic bone agents, or rPTH, such as:	Denosumab, teriparatide, Fosamax®, Fosamax Plus D®, Binosto®, Boniva®, Reclast®, Zometa®, Prolia®, XGEVA®, Forteo®, Actonel®, Atelvia®, Miacalcin®, Fortical®	
Synthetic prostaglandin E1 (PGE1) analogs, such as:	Misoprostol (Cytotec®, Arthrotec®) Single use of PGE1 for cervical preparation prior to biopsy is allowed; chronic use is prohibited.	
Glucocorticoids/corticosteroids, systemic administration (oral, IM, or IV)	Except for short-term use as noted in this protocol. See Section 5.1.	

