All screening laboratory results must be reviewed prior to Baseline, including any repeated test results. Screening laboratory tests may be repeated one time prior to the Baseline Visit; however, results must satisfy entry criteria prior to randomization. Subjects should not be randomized at Baseline Visit if screening laboratory results do not meet entry criteria or the investigator assesses them as clinically significant. The most recent laboratory test results obtained prior to the Baseline Visit predose samples will serve as the Baseline for clinical assessment.

The investigator will receive sponsor-defined alerts from the central laboratory. The investigator will review the lab alerts and assess clinical significance for potential AEs.

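### Statins and other lipid-lowering agents must be washed out before entry, but the legible on-study prohibited list does not name them, so a restart during treatment is not expressly barred

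*Protocol*

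**What the plan says.** Protocol Section 5.1 contains the table titled "Table 1. Washout Intervals for Exclusionary Hormonal/Anti-Hormonal Therapy". One of its last rows is "Statins (and other lipid-lowering agents"). The interval cell for that row is hard to read in the text available to us and appears to be the one-month interval shared with metformin. Criterion 2 makes the Table 1 washouts a condition of entry and is silent on what happens afterwards.

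The ban during the study is written in three places, each by reference to Table 2:

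- Criterion 3: "Subject is not taking exclusionary therapies. The medications listed in Table 2 should not be taken", followed by the study periods.
- Criterion 20, among the things a subject must not be using: "Medications identified in Section 5.3 Table 2 during Washout, Screening, Treatment or Post-Treatment Follow-Up Periods".
- Section 5.3: "The medications listed in Table 2 should not be taken during Washout (if applicable), Screening, Treatment Period, and Post-Treatment Follow-Up Period".

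Table 2 carries over metformin, the neighbour of statins in Table 1: "Metformin or other similar medications, including diabetes". No legible part of Table 2 mentions statins or lipid-lowering drugs.

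Lipids are one component of the metabolic item among the additional endpoints (Protocol Section 3.4). SAP Section 8.5.5 analyses their change from baseline by ANCOVA, and SAP Section 9.3 summarises them again as safety laboratory data. Neither section has a rule for lipid-lowering drugs started on study.

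**The concern.** A washout sets an off-drug reference for later change. If the drug can return during treatment, that subject's post-baseline lipid values mix the effect of study drug with the effect of the restarted agent, and her change score no longer measures what the washout prepared for.

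There is a practical prompt to start. The lipid panel is drawn at Weeks 4, 8, 16 and 24. Under Operations Manual Section 3.19 the investigator receives the results and handles clinically significant values by standard of care. A site that looks up a statin in Table 2 finds no entry. Section 5.4 would have the drug recorded, and the withdrawal rule in Section 5.5 concerns only prohibited medications. Two sites could therefore handle the same woman differently, both in good faith.

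**Working it through.** The point is textual, and the plan gives no figure to reproduce.

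**Step 1: compare Table 1 with the on-study rules.**

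| Table 1 class | On-study counterpart |
|---|---|
| Medroxyprogesterone, oral contraceptives, estrogens, progestins, vaginal ring, danazol | Table 2, hormonal rows |
| GnRH agonists and antagonists | Table 2 |
| Aromatase inhibitors, progesterone receptor modulators, clomiphene, antiandrogens | Table 2 |
| Gonadotropins | Table 2, under infertility treatments and hCG |
| Systemic glucocorticoids | Table 2 and criterion 20 |
| IUDs and implants | Table 2 (hormonal) and criterion 20 |
| CYP3A inducers and inhibitors | Table 2 |
| Metformin and similar agents | Table 2 |
| Statins and other lipid-lowering agents | None found |

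The remaining legible Table 2 classes (OATP1B1 inhibitors, retinoids, drugs affecting bone, osteoporosis drugs, PGE1 analogs, acne treatments) do not cover lipid-lowering agents. The other bullets of criterion 20 do not either.

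**Step 2: illustrate the size.** All clinical inputs here are assumptions, and none is in the documents: LDL-C off therapy of 120 to 140 mg/dL, a fall on therapy of 30% to 40%, a standard deviation (SD) of change of 20 to 30 mg/dL, and 2% to 5% of women starting. The arm sizes of 20 and 30 come from the protocol.

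- Fall per starter: 120 × 0.30 = 36 mg/dL; 140 × 0.40 = 56 mg/dL.
- Standard error (SE) of an elagolix-placebo difference: SD × √(1/20 + 1/30) = SD × 0.2887, which is 5.77 (SD 20) to 8.66 (SD 30).
- Expected starters in 130 women: 130 × 0.02 = 2.6; 130 × 0.05 = 6.5.

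*Equal share p starting in every arm.* The expected difference does not move and only noise is added: SD′ = √(SD² + p(1 − p) × fall²).

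| p | Fall | SD 20 becomes | SD 30 becomes |
|---|---|---|---|
| 2% | 36 | 20.63 (+3.1%) | 30.42 (+1.4%) |
| 2% | 56 | 21.48 (+7.4%) | 31.01 (+3.4%) |
| 5% | 36 | 21.48 (+7.4%) | 31.01 (+3.4%) |
| 5% | 56 | 23.43 (+17.1%) | 32.39 (+8.0%) |

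The SE rises by the same percentages.

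*Unequal starts.* One extra starter in an elagolix arm of 20 shifts the difference by −36/20 = −1.8 to −56/20 = −2.8 mg/dL. Relative to the SE that is 1.8/8.66 = 0.21 to 2.8/5.77 = 0.48. One extra starter in the placebo arm of 30 shifts it by +36/30 = +1.2 to +56/30 = +1.9 mg/dL.

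**The case against.** The best case against the point has four parts.

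**Intent to exclude is visible.** Criterion 3 opens by saying the subject is not taking exclusionary therapies, and Table 1 is the table that bears that word. Section 5.4 calls drugs stopped before dosing prohibited, and it sends questions on concomitant therapy to the sponsor's medical director. A site could reasonably treat a Table 1 drug as barred. This stands as evidence of intent. It does not close the gap, because the next sentence of criterion 3 sets the on-study ban by Table 2.

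**Table 2 reached us damaged.** Its rows are repeated and out of order. The row labels can still be read and no lipid fragment appears, but the finding rests on the legible text and should be checked against the original page.

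**Safeguards already limit the exposure.** Criterion 18 keeps out women with "A clinically significant medical condition anticipated to require intervention during the course of the study participation". Operations Manual Section 3.19 says not to randomize a woman if "screening laboratory results do not meet entry criteria or the investigator assesses them as clinically significant". Diabetes is excluded. SAP Section 9.3 counts potentially clinically significant lipid values at any time on treatment and tabulates worst-value shifts. Section 5.4 collects start and stop dates, and SAP Section 7.3 tabulates use by ATC class and arm. These stand and reduce the importance of the point. They do not protect the change-from-baseline means.

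**It may be deliberate.** Standardizing entry while leaving ordinary care open for 24 weeks is a legitimate design, and the documents never say why statins are washed out. That is possible, but nothing explains why this one class would be treated differently from every other row.

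A reader might go further and infer that Table 2 is the only source of on-study restrictions, or that the protocol permits a restart. Neither is supported. Criterion 20 has limits of its own on corticosteroids, IUDs and implants, and silence in Table 2 is a drafting gap rather than permission.

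**Conclusion.** The mismatch between the two tables holds on the legible text. It is minor. A restart or elective start is not expressly barred, and it would distort lipid change from an off-drug Baseline for the women concerned. The primary endpoint (menstrual cycle response) and the key secondary endpoint (LH AUC at Week 1) are unaffected.

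The size cannot be derived from the documents. The ranges above rest wholly on the stated assumptions. The 17% rise in SE combines the highest share of starters, the largest fall and the smallest SD, with every starter at full effect. Use is likely uncommon at ages 18 to 35, so the low end (a rise of 1.4% to 7.4% at 2% starters) is more plausible, and the true effect is probably very small.

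Two readings about bias should be avoided. One is that randomization and blinding make any starts balanced, so that only noise is added. That is not shown, because investigators see and act on on-treatment lipid results. If lipids rose more in one arm, more starts could follow there and pull its mean change down. The other is that the lipid comparison is biased. The documents give no starting rates by arm, so no direction or amount can be claimed.

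**What to change.** Add a lipid-lowering row to Table 2 for the Washout, Screening and Treatment Periods, with an exception for a medically necessary start that is recorded as a concomitant medication. Keep the lipid analyses on all observed values as planned. A by-arm listing of starters with start dates is optional. It would use dates already collected and would show timing against the lipid visits, which the planned ATC counts do not.

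The cost is one table row and, if wanted, one short listing. The downside is a 24-week restriction on an uncommon concomitant therapy. The row would stop elective starts and restarts only. Medically necessary starts would still occur, and those are the ones least safely assumed to be balanced.
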